9.5 Does the protocol specify timelines for				
9.5.1 Study start?				18
9.5.2 Study progress? (e.g. end of data collection, other milestones)				18
9.5.3 Study completion?				18
9.5.4 Reporting? (i.e. interim reports, final study report)				18
9.6 Does the protocol include a section to document future amendments and deviations?				
9.7 Are communication methods to disseminate results described?				36
9.8 Is there a system in place for independent review of study results?				Steering Committee

Comments:

--

Section 10: Ethical issues	Yes	No	N/A	Page Number(s)
10.1 Have requirements of Ethics Committee/Institutional Review Board approval been described?				32
10.2 Has any outcome of an ethical review procedure been addressed?				
10.3 Have data protection requirements been described?				32/33

Comments:

--

Name of the coordinating study entity: Bayer HealthCare, Global Non-Interventional Studies

Date: 04/07/2013

Signature: \_\_\_\_\_

A legal person, institution or organization which takes responsibility for the design and/or the management of a study.

## 16. Annex 4. Additional information.

### 16.1. BCLC Staging System

[figure not shown]

Figure 2: BCLC staging and treatment strategy

## 16.2. Performance Status (PS) (Eastern Cooperative Oncology Group [ECOG])

Grade	Description
0	Fully active, able to carry on all pre-diseases performance without restriction. (Karnofsky 90-100)
1	Restricted in physically strenuous activity but ambulatory and able to carry out work of a light or sedentary nature (eg, light housework, office work). (Karnofsky 70-80)
2	Ambulatory and capable of all self-care but unable to carry out any work activities. Up and about more than 50% of waking hours. (Karnofsky 50-60)
3	Capable of only limited self-care, confined to bed or chair more than 50% of waking hours. (Karnofsky 30-40)
4	Completely disabled. Cannot carry on any self-care. Totally confined to bed or chair. (Karnofsky 10-20)

## 16.3. TNM Classification

### Primary tumor (T)

- TX: Primary tumor cannot be assessed
- T0: No evidence of primary tumor
- T1: Solitary tumor without vascular invasion
- T2: Solitary tumor with vascular invasion or multiple tumors none more than 5 cm
- T3a: Multiple tumors >5cm
- T3b: Single tumor or multiple tumors of any size involving a major branch of the PV or HV
- T4: Tumor(s) with direct invasion of adjacent organs other than the gallbladder or with perforation of the visceral peritoneum

### Regional lymph nodes (N)

- NX: Regional lymph nodes cannot be assessed
- N0: No regional lymph node metastasis
- N1: Regional lymph node metastasis

[Note: The regional lymph nodes are the hilar (i.e., those in the hepatoduodenal ligament, hepatic, and periportal nodes). Regional lymph nodes also include those along the inferior vena cava, hepatic artery, and portal vein. Any lymph node involvement beyond these nodes is considered distant metastasis and should be coded as M1. Involvement of the inferior phrenic lymph nodes should also be considered M1.]

### Distant metastasis (M)

- MX: Distant metastasis cannot be assessed
- M0: No distant metastasis
- M1: Distant metastasis

### AJCC Stage Groupings

- Stage I            T1, N0, M0
- Stage II            T2, N0, M0
- Stage IIIA        T3a, N0, M0
- Stage IIIB        T3b, N0, M0
- Stage IIIC        T4, N0, M0
- Stage IVA        Any T, N1, M0
- Stage IVB        Any T, Any N, M1

## 16.4. Liver Status – Child-Pugh Classification

### Points Scored for Observed Findings

	Points Scored for Observed Findings		
	1	2	3
Encephalopathy grade a	None	1 or 2	3 or 4
Ascites	Absent	Slight	Moderate
Serum bilirubin, mg/dL	< 2	2 to 3	> 3.0
Serum albumin, g/dL	> 3.5	2.8-3.5	< 2.8
Prothrombin time, sec (prolonged)	< 4	4-6	> 6

a \*Encephalopathy grades:

Grade 0: normal consciousness, personality, neurological examination, electroencephalogram

Grade 1: restless, sleep disturbed, irritable/agitated, tremor, impaired handwriting, 5 cps waves

Grade 2: lethargic, time-disoriented, inappropriate, asterixis, ataxia, slow triphasic waves

Grade 3: somnolent, stuporous, place-disoriented, hyperactive reflexes, rigidity, slower waves

Grade 4: unrousable coma, no personality/behavior, decerebrate, slow 2-3 cps delta activity

Assessment as good operative risk (A) if 5 or 6 points; moderate risk (B) if 7 to 9 points, and poor operative risk (C) if 10 to 15 points (developed for surgical evaluation of alcoholic cirrhotics).

## 16.5. RECIST Criteria

### Modified RECIST (mRECIST)

Response and progression should preferably be evaluated in this study using a modified version of RECIST version 1.1, which combines quantitative assessment of a set of lesions using unidimensional measurements with qualitative assessment of all other lesions (Eisenhauer EA et al.; New response evaluation criteria in solid tumours: Revised RECIST guideline (version 1.1). EJC 2009 45:228-247).

The modifications introduced for the assessment of intrahepatic lesions are based on the modified RECIST criteria published in 2010 for the assessment of hepatocellular carcinoma (Lencioni R and Llovet JM; Modified RECIST (mRECIST) Assessment for Hepatocellular Carcinoma. Sem Liver Dis 2010 30;1:52-60).

Results from a number of previous clinical studies in HCC have demonstrated that RECIST does not adequately capture the extent of tumor necrosis induced by interventional therapies or new molecular targeting drugs. Only viable tumor, assessed by properly designed CT or MRI studies, should be included in the tumor burden, and viable tumor should be defined as uptake of contrast agent in the arterial phase of dynamic imaging studies. Consequently, a modification of RECIST was first proposed by a panel of experts, and further expanded. This proposal is based on the fact that the diameter of the target lesions with viable tumor tissue should be the basis of measurements for intrahepatic lesions. In addition, there are specific modifications of the original criteria regarding the assessment of vascular invasion, lymph nodes, ascites, pleural effusion, and new lesions. (Llovet JM, et al.; Panel of Experts in HCC-Design Clinical Trials: Design and Endpoints of Clinical Trials in Hepatocellular Carcinoma. J Natl Cancer Inst. 2008 May 21;100(10):698-711)

The expert panel has adopted the concept of viable tumor endorsed by European Association for the Study of the Liver (EASL) and proposed amendments (Llovet JM, et al. 2008) to RECIST in the determination of tumor response for HCC, which have been incorporated into the criteria in this trial as described herein.

### Definitions

Intrahepatic lesions: Malignant findings within the liver parenchyma, the portal vein, and the porta hepatis region. The rules for the assessment of intrahepatic lesions (including when a new lesion is considered to have appeared) incorporate the referenced modifications for HCC.

Extrahepatic lesions: All malignant lesions, other than those defined as intrahepatic as above. These lesions will be assessed using the standard RECIST 1.1 approach.

Measurable lesions: Lesions that, at baseline, meet the requirements for being reproducibly quantifiable. The requirements are different for intrahepatic and extrahepatic lesions, and are described below. Lesions that meet the requirements are considered eligible for quantitative assessment during the study.

Non-measurable lesions: Lesions that, at baseline, do not meet the below-described requirements, cannot be chosen for quantitative assessment, and must be assessed qualitatively.

Target lesions: Lesions that are chosen at baseline (from the set of measurable lesions) for quantitative assessment throughout the trial, using rules outlined below. A lesion that has been selected as a target lesion remains a target lesion for the rest of the trial.

Non-target lesions: Lesions that are not chosen at baseline for quantitative assessment, and must be assessed qualitatively throughout the trial. A lesion that has been selected as a non-target lesion remains a non-target lesion for the rest of the trial.

Typical HCC enhancement: A lesion is considered to have typical HCC enhancement if it shows enhancement during the arterial phase of contrast administration, with washout in the portal venous or late venous phase.

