## Baseline Assessment

### Identifying measurable disease:

*Non-nodal tumor lesions:* Measurable lesions are those that can be accurately measured in at least one dimension (longest diameter to be recorded) with a minimum size of:

- 10 mm by CT scan (CT scan slice thickness no greater than 5 mm) or MRI. If scans with slice thickness greater than 5mm are used, the minimum size should be twice the slice thickness.
- 20 mm by chest x-ray
- 10 mm caliper measurement by clinical examination (lesions which cannot be accurately measured with calipers should be recorded as non-measurable)
- For lesions within the liver parenchyma, only the portion of the lesion that shows typical HCC enhancement should be included in the measurement.

*Malignant lymph nodes:* To be considered pathologically enlarged, a lymph node must be  $\geq$  10 mm in short axis when assessed by CT scan (except nodes in the porta hepatis – see below). To be considered measurable, a lymph node must be  $\geq$  15 mm in short axis when assessed by CT scan.

*Lytic bone lesions or mixed lytic-blastic lesions,* with identifiable soft tissue components that can be evaluated by CT or MRI, can be considered as measurable lesions if the soft tissue component meets the definition of measurability.

Tumor lesions situated in a previously irradiated area are not considered measurable unless there has been demonstrated progression in the lesion.

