#### Target lesion assessment

The investigator will measure each target lesion in the same manner as at baseline. Extrahepatic non-nodal lesions will be measured using their longest diameter. Malignant lymph nodes (excluding those in the porta hepatis, which can never be target lesions) will be measured in short axis diameter. Intrahepatic target lesions will be measured in the longest diameter that shows typical HCC enhancement (excluding areas of necrosis).

If a lesion decreases in size to the point where it is still present, but cannot be measured accurately, a default value of 5 mm should be recorded for its diameter. If a lesion has disappeared, a value of 0 mm should be recorded for its diameter. If a lesion has split into distinct fragments, the longest diameter of each fragment should be measured, and the diameters added together. If two lesions have merged, the longest diameter of the entire resulting lesion should be measured.

The sum of diameters will be calculated by adding all target lesion diameters. The sum of diameters is always compared to two reference points: the baseline sum of diameters, and the smallest sum of diameters seen during the trial (also called the nadir). The baseline may actually be the nadir, if there has been no reduction in the sum of diameters during the trial. The target lesion response is then classified as follows:

Target lesion response	
Complete response (CR)	Complete disappearance of target lesions outside the liver Complete disappearance of typical HCC enhancement from all target liver lesions All target lymph nodes <10 mm
Partial response (PR)	At least a 30% decrease in the sum of diameters from baseline
Progressive disease (PD)	At least a 20% increase in the sum of diameters from the smallest value seen during the trial (including baseline), with at least a 5 mm absolute increase in the sum
Stable disease (SD)	Neither enough shrinkage to qualify as PR, nor enough growth to qualify as PD
Non-evaluable (NE)	One or more target lesions not evaluated because of imaging issues, coverage, or change in imaging technique
Please note that when lymph nodes are included as target lesions, a CR may occur even when the sum of diameters is not zero, since a normal lymph node will have a diameter greater than zero but less than 10 mm.	

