### Non-target lesion assessment

Non-target lesions are assessed as a whole. After examining each non-target lesion, the investigator will classify the non-target lesion response as follows:

Non-target lesion response	
Complete response (CR)	
Complete disappearance of non-target lesions outside the liver
 
Complete disappearance of typical HCC enhancement from all non-target liver lesions
 
All non-target lymph nodes <10 mm
 
Resolution of malignant portal vein thrombosis (if present)

Progressive disease (PD)	Unequivocal progression of non-target lesions as a whole
Non-CR/Non-PD	Non-target lesions still present, without unequivocal progression
Not all evaluated	One or more non-target lesions not evaluated because of imaging issues, coverage, or change in imaging technique

To achieve unequivocal progression in patients with measurable disease on the basis of the non-target disease, there must be an overall level of substantial worsening in non-target disease such that, even in presence of SD or PR in target disease, the overall tumor burden has increased sufficiently to merit discontinuation of therapy. A modest ‘increase’ in the size of one or more non-target lesions is usually not sufficient to qualify for unequivocal.

Cytopathologic confirmation of the neoplastic nature of any effusion that appears or worsens during treatment is required to declare PD.

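### The mRECIST annex defines viable liver tumor by arterial uptake, but measures it and judges complete response by arterial uptake plus washout

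*Protocol*

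**What the plan says.** All of this is in Protocol Annex 4, section 16.5 (RECIST Criteria).

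- **Modified RECIST (mRECIST), introduction.** The annex limits what is counted: "Only viable tumor, assessed by properly designed CT or MRI studies, should be included in the tumor burden". The definition that goes with this limit reads: "viable tumor should be defined as uptake of contrast agent in the arterial phase of dynamic imaging studies". Washout is not mentioned. The expert panel's amendments built on the viable-tumor concept are described as ones "which have been incorporated into the criteria in this trial as described herein".
- **Definitions.** A lesion has typical HCC enhancement if "it shows enhancement during the arterial phase of contrast administration, with washout in the portal venous or late venous phase".
- **Identifying measurable disease.** For lesions in the liver parenchyma, "only the portion of the lesion that shows typical HCC enhancement should be included in the measurement".
- **Target lesion assessment.** The follow-up diameter of liver targets rests on the same term. The liver condition for target CR is "Complete disappearance of typical HCC enhancement from all target liver lesions".
- **Non-target lesion assessment.** The parallel condition is "Complete disappearance of typical HCC enhancement from all non-target liver lesions".
- **Text descriptions after the visit-response tables.** These are declared equivalent to the tables. CR there means that no tumor remains on either clinical or radiological evidence. Progression can rest on growth of liver lesions with *typical arterial enhancement*, a third term that does not mention washout.

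Protocol section 9.3.9 makes mRECIST the preferred scale. Other criteria are allowed where a site does not use mRECIST routinely.

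**The concern.** The introduction fixes what counts as tumor, and the operative rules then measure something narrower. Treated liver tissue that still takes up contrast in the arterial phase but no longer washes out is viable under the introduction, yet outside the diameter under the measurement rules. Two readers of one scan can each cite the annex for a different category.

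Response by mRECIST is a secondary endpoint for each TACE and for visits on sorafenib (section 9.1.2). Section 16.5 also names mRECIST as the preferred basis for progression, which enters PFS and TTP. Response to the most recent TACE is listed in section 9.7.8 as a possible confounder for the propensity score. If sites or regions resolve the ambiguity differently, response rates and progression dates differ for reasons unrelated to treatment.

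**Working it through.** The plan states no figure on this point, so there is none to reproduce. The check traces the rules and then scores assumed lesions.

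**1. One kind of tissue under each rule.** Take a known liver lesion that enhances arterially without washout.

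| Place in section 16.5 | Standard used | Result for this tissue |
|---|---|---|
| mRECIST introduction | arterial uptake | viable, counts in tumor burden |
| Identifying measurable disease | arterial plus washout | not in baseline diameter |
| Target lesion assessment, diameter | arterial plus washout | not in follow-up diameter |
| Target and non-target CR, liver | arterial plus washout gone | compatible with CR |
| Text description of CR | no radiological tumor left | not CR |
| Text on progression | typical arterial enhancement | growth can count as progression |

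The table gives conflicting answers for the same tissue.

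**2. Effect on response category.** Assumed sizes, not from the documents: two liver targets of 40 and 30 mm at baseline, with the same tissue still enhancing arterially at follow-up. Change = 100 × (follow-up sum / baseline sum − 1), with a baseline sum of 40 + 30 = 70 mm. Partial response needs a fall of at least 30%.

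- Arterial uptake only: sum 70 mm, 70/70 − 1 = 0%. Stable disease.
- Typical enhancement, washout lost in the 30 mm lesion: sum 40 mm, 40/70 − 1 = −42.9%. Partial response, not CR.
- Typical enhancement, washout lost in both: sum 0 mm, −100%. The target CR wording for liver lesions is met.
- The same, but with the 5 mm default recorded for each lesion: sum 10 mm, 10/70 − 1 = −85.7%. The liver CR wording is still met, because it rests on enhancement and not on the sum.

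CR for the visit also needs CR of any non-target lesions and no new lesion.

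**3. Effect on progression.** Progression on target lesions needs a rise of at least 20% and at least 5 mm over the smallest sum.

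- Assume one lesion of 50 mm whose arterial enhancement grows to 62 mm without washout. By arterial uptake, 62/50 − 1 = +24% and +12 mm, which is progression. By typical enhancement, this tissue is not measured.
- The error can run the other way. In the two-lesion case with a smallest sum of 40 mm, return of washout in the unchanged 30 mm lesion gives 70/40 − 1 = +75% and +30 mm. That is progression without growth.

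**4. Lesions without washout from the start.** The catch-all under Identifying non-measurable disease takes them in, so they are followed as non-target lesions. The liver wording for non-target CR is then already satisfied at baseline.

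**5. Reach.** The primary endpoint in section 9.1.1 is death from any cause after TACE non-eligibility. The criteria in section 9.3.8 do not refer to mRECIST categories.

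**The case against.** The best defence is that the introduction only summarises an expert proposal, and that the detailed rules are what readers follow. Those rules have safeguards. The explicit 0 mm rule covers lesions that have disappeared. CR in the text description cannot coexist with visible residual tumor. The progression text does not require washout. Under New lesions, a radiological event is dated back to its first detection.

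These points limit the consequence but do not remove the contradiction. The introduction claims that the viable-tumor amendments are built into the criteria, and the detailed rules disagree among themselves.

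The safeguards do rule out four stronger readings that a reader might infer:

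- **That such tumor is always scored 0 mm and counted as CR.** The 0 mm value is an inference from the measurement rule. CR needs every target and non-target liver lesion to qualify and no new lesion, and the CR text points the other way. The 62 mm example likewise has textual support for progression.
- **That lesions without washout fall into no category.** The catch-all makes them non-measurable.
- **That the inflation of the CR rate can be stated.** With an assumed true CR rate of 30%, and 5%, 10% or 20% of the remaining patients lacking washout, 0.30 + 0.70 × w gives 33.5%, 37% or 44%. These are upper bounds on assumed inputs, because they turn every affected patient into a CR.
- **That overall survival is biased by this.** The endpoint does not use these rules.

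The documents also do not say that washout is clinically irrelevant to viability. The point rests only on the annex's own definition.

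**Conclusion.** The inconsistency is real and should be corrected. For known liver lesions, section 16.5 uses one standard for what viable tumor is, a narrower one for diameter and CR, and further wording for overall CR and progression. On a literal reading of the measurement rules, tissue that the annex calls viable can be left out. This turns stable disease into partial response if some lesions lose washout, and can satisfy the liver CR wording if all do.

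The reach is tumor response and radiological progression in PFS and TTP at sites using mRECIST. It may extend to one possible propensity covariate, and so indirectly to the adjusted comparison. The size cannot be estimated, because the documents give no frequency of arterial enhancement without washout. The worked sizes are illustrations.

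**What to change.** Use one enhancement standard for known liver lesions in section 16.5: the arterial-uptake definition of viable tumor that the introduction says is incorporated. Apply it under Identifying measurable disease, Identifying non-measurable disease, Target lesion assessment and Non-target lesion assessment. Apply it also in the text descriptions of CR and progression, so that they match the tables. Keep arterial enhancement plus washout only under New lesions, for classifying a new liver nodule as HCC.

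The cost is annex wording and a short reading note to sites. No extra imaging is needed, because Methods of Measurement already calls for an arterial phase. The small downside is that some benign arterial enhancement after treatment may be read as viable tumor, so the CR rate may be slightly lower.

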## **Methods of Measurement**

All measurements must be recorded in millimeters (or decimal fractions of centimeters).

For measurements of tumors other than lymph nodes, the longest unbroken diameter seen on an axial slice is recorded. Lymph nodes must always be measured in the short axis (the longest measurement on an axial slice perpendicular to the longest diameter of the lymph node). Lymph nodes less than 10 mm in short axis diameter are defined as normal.

The cytological confirmation of the neoplastic origin of ascites or pleural effusion that appears or worsens during treatment when the subject has met criteria for response or stable disease is mandatory to differentiate between response or stable disease (an effusion may be a side effect of the treatment) and progressive disease.

The same method of assessment and the same technique should be used to characterize each identified and reported lesion at baseline and during follow-up.

Clinical Lesions - Clinical lesions will only be considered measurable when they are superficial (e.g. skin nodules, palpable lymph nodes) and  $\geq 10$ mm diameter as assessed using calipers. For the case of skin lesions, documentation by color photography including a ruler to estimate the size of the lesion is recommended.

Chest X-ray - Lesions on chest X-ray are acceptable as measurable lesions when they are clearly defined and surrounded by aerated lung. However, chest CT is preferable.

CT / MRI - CT is the best currently available and reproducible methods to measure target lesions selected for response assessment. CT scans should be performed with cuts of 5 mm or less in slice thickness. For assessment of the liver, a three phase enhancement protocol is required, which includes scans prior to contrast administration, during the arterial phase of contrast, and during the portal venous or delayed (systemic venous) phase. MRI is also acceptable. This applies to the chest, abdomen and pelvis. Head & neck and extremities usually require specific protocols.

Ultrasound - Ultrasound is not useful in assessment of lesion size and should not be used as method of measurement. If new lesions are identified by ultrasound in the course of the study, confirmation by CT or MRI is advised.

Endoscopy / Laparoscopy - The use of these techniques for objective tumor evaluation is not advised.

Cytology / Histology - These techniques can be used to differentiate between PR and CR in rare cases.

